#### 7.3 Stop Points

It is recognized that certain situations may require premature discontinuation of the randomized therapy (stop-points). Provided the subject does not withdraw consent and is not lost to follow-up, data collection and follow-up will continue for all subjects meeting any of the following stop-points in order to perform the intent to treat analysis. Wherever possible and clinically appropriate, efforts should be made by the treating physician and principal investigator to get the patient back into their randomized group. All discontinuations of therapy will be reviewed by the Standards of Care/Clinical Management Committee, and all participants who permanently discontinue therapy will be interviewed regarding the reasons for discontinuation. Subjects may discontinue the randomized therapy for the following reasons:

- a) The treating physician determines that the subject requires more frequent or less frequent dialysis for reasons including, but not limited to, the following: uremic symptoms, uncontrolled hypertension, patient fatigue/burnout, etc.
- b) The subject changes from in-center hemodialysis to home hemodialysis. Where possible, recommendations will be made to continue the subject on their assigned

treatment frequency (i.e., in-center daily will change to home daily HD; in-center conventional will change to home conventional HD).

#### 7.4 Losses to Follow-up

Efforts will be made to follow all randomized subjects for 12 months, irrespective of their adherence to the randomized therapy. However, certain situations may preclude complete data collection for the full 12 months (losses to follow-up).

The randomized therapy and routine data collection will be discontinued in the following situations:

- a. Subject withdraws consent for data collection
- b. Subject changes to peritoneal dialysis
- c. Subject receives renal transplant
- d. Subject relocates to a non-study center.
- e. Subject changes to home HD.

For patients who are lost to routine data collection for reasons b - e above, all attempts will be made to collect vital status. For patients who are lost to routine data collection for reasons d and e above, all attempts will be made to collect vital status, the primary and main secondary outcomes, and other centrally administered quality of life questionnaires at the 12-month visit.

All losses to follow-up with reason will be reported to the DCC (discontinuation of therapy form). The Adherence Committee will review all losses to follow-up on a monthly basis.

#### 8. Economic Evaluation

#### 8.1 Hypothesis

We hypothesize that savings in non-dialysis health care costs due to better health from daily hemodialysis will offset its additional dialysis related expenses. That is, we hypothesize that daily hemodialysis will be a "Dominant Strategy" (better outcomes with reduced costs).

#### 8.2. Purpose

If daily hemodialysis proves to be cost-effective, it will be important to understand:

- a) The changes in dialysis center costs to provide this mode of hemodialysis,
- b) The changes in overall health care costs to insurers (primarily CMS) of patients using this mode of hemodialysis,
- c) The cost-effectiveness of the intervention (change in insurer costs per change in quality adjusted life-years).

The purpose of the economic analysis in this trial is to provide answers to these questions.

#### 8.3 Data Collection and Methods

Resource use for patients assigned to either arm of this study will be assessed under the various headings, and by the methods listed in the tables below. Additionally, the following data will be available for economic and other analyses:

- Baseline income and employment status
- Follow up income and employment status

- Baseline vascular access
- All follow up vascular access replacement, repair or removal

*General*. To obtain estimates of cost independent of year and geographical differences, we will denominate the use of resources initially in terms of more basic units: hours of nursing or other professional time, outlier adjusted DRG weights for hospitalizations and Medicare allowable charges for other types of payments, specific classes of equipment needed for dialysis and actual supplies used, actual non-injectable drug prescriptions. These will then be given dollar values using consistent references such as published salary scales, national average payments for diagnosis related groups (DRGs) for hospital services and relative value units (RVUs) for professional services, General Services Administration (GSA) contract prices, Red Book average wholesale prescription prices or Average Sales Price (ASP).

Resource use for patients assigned to either arm of this study will be assessed under the various headings, and by the methods listed in the Tables 12 - 14 below.

Cost element	Method of assessment	Calculation of standard cost
"Dialysis Unit Shifts, Staffing, and Equipment" at each dialysis station (1)	Compiled by a subset of dialysis administrators. Collected starting eight months after the first patient has been randomized.	For shifts and staffing, cost is calculated using published salary scales. For equipment, cost is calculated using the GSA price list, with amortization period determined by consensus. Cost per dialysis will be computed.
"Costs of machines and supplies"	Collected starting eight months after the first patient has been randomized	Costs are recorded.
Routine laboratory tests included in "bundle."	Published charges by large reference laboratories.	Inflation adjusted average published permitted charge.
Overhead	Average overhead from CMS cost reports.	Applied as a percent to total of above.

 Table 12: Costs per Dialysis of In-center Dialysis (6 or 3 Times Weekly)

Comments:

(1) We anticipate that larger Clinical Centers with a higher fraction of subjects on daily dialysis may be able more frequently than smaller units or units with few daily patients to assign more than the usual number of daily patients to one station, thereby increasing the number of dialyses per station per day and reducing per dialysis station costs. If daily dialysis proves advantageous, this practice is likely to evolve over time. Rather than trying to estimate the impact of this possibility during the course of this trial, we will model this issue based on observed ratio of dialysis time to clean-up/set-up time (from the time and motion study) and stipulated unit sizes and fractions of patients on daily hemodialysis. This modeling will be used for sensitivity analyses of the per dialysis costs of station equipment.

Cost element	Method of assessment	Calculation of standard cost
Injectable medicines	Recorded at multiple time points.	Medicare allowable charges for the various agents and doses.
Hospitalizations (Part A)	Estimated from claims for Medicare primary patients in study cohort. Record of ICD9 Diagnostic and Procedure Codes (or Canadian equivalent) and length of stay for all hospitalizations for patients in Medicare HMOs and Canada.	Consistent assignment of DRGs for each hospitalization (with duration adjustment), using "DRG grouper" and related standardized CMS payments.
Hospitalizations (Part B)	Estimated from claims for Medicare Primary patients in study cohort. Total Part B allowed charges corresponding to known dates of hospitalization.	Attribute charges for Medicare Primary to non- Medicare Primary patients with the same DRGs. Standard CMS payments per RVU.
Outpatient medications (Part D)	Data from Form 205 completed at Baseline, F4, F8 and F12. Can be crosschecked with data from pharmacy records maintained for Part D expenditures in Medicare patients.	Assign set cost for each medication based on average wholesale price or average sales price.
Non-hospital Medicare covered services	Estimated from claims for Medicare primary payer patients. Data from form 208 and 209 collected at Baseline, F4 and F12. Can be crosschecked with claims data from CMS.	Assignment of CMS HCPCS codes. Standard CMS payments.

 Table 13: Other CMS Covered Medical Care

Comments: In principle, it would be possible to obtain non-dialysis Medicare charges directly from the CMS billing data. However, participants in this trial may be Canadian, members of an HMO (in California), or within the first three years of ESRD on other than Medicare Primary insurance

coverage. Therefore we draw inferences from hospital stay data collected within the trial itself. These data include major diagnostic group for the stay, which is used in Medicare pricing. We shall check validity of estimation process by comparing estimates with the actual billed charges in the subset of patients that is Medicare Primary.

Cost element	Method of assessment	Calculation of standard cost
Non-injectable medicines (not covered by Medicare Part D)	Data from Form 205 completed at Baseline, F4, F8 and F12 and crosschecked with Part D data.	Prices calculated from "Red Book."
Patient employability or other socially productive activities	Data from Form 105 (at baseline) and Form 233 (at F12).	"Social functional status" recorded and compared.

Table 14: Other Health Care Related Expenses Not Covered by Medicare

#### 8.4 Analysis Plans

- a) **Intention to treat**: All analyses will be performed on an "intention to treat" basis. That is, the average costs of subjects in each arm will be determined retaining all subjects in their originally randomized arm, irrespective of the treatment that is ultimately used for that subject. If a subject is lost to the trial by death, transplantation, withdrawal of consent, or move to a non-participating center, that subject will be included in his/her original randomization group, but the costs will be pro-rated for the actual time in the trial.
- b) **Sensitivity analysis**: An important component of any economic evaluation is an analysis of the uncertainty surrounding the differences in expected costs and expected utility of the alternative strategies. Our approach to the analysis of uncertainty will be informed by the guidelines of the Panel on Cost-Effectiveness in Health and Medicine (Gold et al, 1996):
  - Conduct univariate (one-way) sensitivity analysis for all variables to determine where uncertainty about some key parameters could have a substantial impact on the conclusions. A tornado diagram will be used to sort the variables by their magnitude of effect (sensitivity). The potential sensitive parameters include rate of hospitalization, cost for a hospital stay, EPO dose and rate of EPO use, weekly nursing time within the facility, facility capacity, proportion of frequent to all dialysis patients, and various techniques to allocate overhead to each modality. For the lifetime analysis, additional sensitive parameters include technique survival (length of time on randomized modality), patient survival, and discount rate.
  - Conduct multivariate (2- or 3-way) sensitivity analysis for important parameters. This explores potential magnitude of effect when two or more key parameters are altered together. The results from univariate sensitivity analysis will serve as a guide to select the variables in multivariate sensitivity analysis. The potential

sensitive parameters pairs may include hospital costs and rate of hospitalizations, or EPO dose and rate of EPO use.

• Construct a confidence or credible interval around the cost-effectiveness result. Bootstrap simulation with replacement will be utilized to derive costs and utilities and associated incremental cost effectiveness ratio (ICERs) with 95% confidence intervals. Acceptability Curves will be constructed to determine the probability of daily hemodialysis being cost-effective over the standard hemodialysis under certain cost-effectiveness thresholds. Conventionally, ICERs of less than \$50,000 per QALY are considered very cost-effective whilst those with an ICER of between \$50,000 and \$100,000 per QALY are considered moderately costeffective

In addition, the estimates from physician reported utilizations will be incorporated for sensitivity analysis.

- c) **Time-frame for analysis**: The economic evaluation will consider two time-frames: a) within trial one-year period, and b) the lifetime of the patient. We recognize specifically that the costs of the non-dialysis component of care may decline over the year of observation, such that the average over the year might underestimate the long-term impact on costs (and benefits). This will be assessed by estimating total costs within the first and the final four months of the study. We shall use a probabilistic economic model to project long-term survival, health benefits, and costs beyond the study period and extend the findings to patients and facilities not included in the trial. Lifetime costs and benefits will be **discounted at a rate of 3%**. See Appendix 4 for additional details.
- d) Objective 1 Costs of dialysis: Costs per month of dialysis for patients in the two study arms will be determined by summing the per dialysis costs of dialysis and multiplying this sum by the average number of outpatient dialysis sessions per month for the patients in each arm of the study. This analysis may be useful to CMS and other payers in setting appropriate payment rates for daily hemodialysis.
- e) **Objective 2 Total CMS covered costs**: Costs per month of CMS covered care will be summed by summing the average per month costs of dialysis (as in (d) above) and of other covered care as in Table 13 above.
- f) Objective 3 Cost-Effectiveness: The impact of randomization to daily hemodialysis (compared with standard 3 times weekly hemodialysis) on life expectancy will be determined directly from survival of patients in the two arms of this trial. Utility (quality of life) will be determined from the Health Utilities Index. The impact of assigned treatment on quality adjusted life years will be calculated from the measures. If as hypothesized, daily hemodialysis is a "dominant" strategy, improving survival/health utility and lowering costs, differences in survival, utility, dialysis costs, and total CMS costs will be presented in a cost-consequences framework. If, conversely, survival/health utility is improved, but total CMS costs are increased, we will calculate the incremental cost-effectiveness ratio (cost per qualityadjusted-life-year), to permit comparison with other possible ways for CMS to spend its health care dollar.

g) Objective 4 - Comparison of short daily with nocturnal hemodialysis: While not a primary purpose of this randomized trial, there will be interest in comparing the FHN Daily Protocol Version 2.3.1: July 2, 2008

outcomes of daily in-center dialysis with the outcomes of overnight nightly home hemodialysis, being studied in the companion trial performed by this Consortium Core. These results will not be directly comparable as the patient groups from which patients will be randomized are different. However the degree of difference (or conversely, of comparability) may be estimated by comparison of the outcomes in the standard arm (in-center hemodialysis three times weekly) in this trial and in the companion trial. We shall make such comparisons.

- h) Power: We acknowledge that the power for some of the above proposed analyses is likely to be low. Specifically, formal power analyses have suggested that there will be low power to detect differences in survival and the rate of hospitalizations, unless the effects of the intervention are far more potent than we have anticipated. Hospitalizations account for 50% more costs than dialysis itself (absent dialysis-related medications); therefore modest changes in hospitalization may yield significant differences in total costs. Therefore a major focus of this economic analysis will be the sensitivity analysis to determine robustness of our analyses.
- i) **Objective 5 Economic and social impact of daily short hemodialysis on the patient:** Information on these aspects of the economic impact of SDHD is likely to be considerably more subjective and less quantitative than for the above components of the economic analysis. We shall therefore make no attempt to merge these data with the economic analyses above, but will rather simply list the conclusions together with the other information in the cost-consequences framework.

### 9. Statistical Analyses

### 9.1 General Methods for Descriptive Summaries and Baseline Comparisons

Quantitative variables will be summarized with standard descriptive statistics and represented graphically with displays such as box plots, smooth density function estimates [Silverman, 1986] and histograms, and categorical variables will be described by frequency tables and standard graphical displays. Inferential analyses for quantitative variables will be performed using 2-group t-tests and, when appropriate, linear models such as analysis of variance and regression. Highly skewed variables may be transformed prior to inferential comparisons, or nonparametric methods employed. Categorical variables will be analyzed with 2-sample comparisons of proportions, logistic regression, general multinomial response models, and ordinal logistic models for ordered categorical outcomes [Agresti, 2002].

#### 9.2 Analyses of Recruitment Process

Descriptive summaries of clinical and demographic characteristics will be obtained for each of the stages of the recruitment process. The characteristics of each stage will be compared to each other and to the USRDS to address the representativeness of the FHN participants. Reasons for exclusion or dropout during baseline will be tabulated.

#### 9.3 Primary Outcomes

The primary analysis will evaluate the effects of the treatment interventions on two co-primary endpoints: 1) a PHC/Mortality composite endpoint based on mortality during the 1-year follow-up period and the change from baseline to 12 months in the SF-36 Rand Physical Health Composite (PHC) among those who survive to 12 months, and 2) a LV mass/Mortality composite based on mortality during the 1-year follow-up period and the change from baseline to 12 months in the Left Ventricular Mass (LV mass) as estimated by cardiac MRI among those who survive to 12 months.

The analysis of the PHC/Mortality composite will be conducted using a rank-based nonparametric procedure as follows. Patients who die prior to 12 months are ranked from lowest (indicating the poorest outcome) to highest based on their survival time prior to death. Those who survive to 12 months are ranked based on the change in the PHC score from baseline to 12 months. The patient with the largest decline in the PHC is given the next lowest rank above the patient with the latest death prior to 12 months. The patient with the largest increase in the PHC is given the highest rank, with the others falling in between. Follow-up is censored prior to 12 months if the patient is transplanted or lost to follow-up for mortality prior to the 12 assessment, and at 12 months if the patient survives to 12 months, but does not provide a 12-month PHC measurement. In this way, if a patient survives to 12 months. The ranks will be compared between treatment groups using the log-rank test which allows the integration of both survival time and a quantitative measure (e.g., the change in PHC score) in the same outcome.

The LV mass/Mortality composite will be analyzed in an analogous fashion, except that increases in LV mass will be given lower ranks (indicating a less favorable outcome) than decreases.

A variation of the Bonferroni correction due to Hochberg [Hochberg, 1988] will be used to assure that the upper limit of the studywise Type I error is approximately 0.05 for the co-primary outcomes. In this procedure both of the co-primary endpoints are regarded as statistically significant if the p-values for both outcomes are not greater than 0.05. If the larger of the two p-values is greater than 0.05, then the outcome with the smaller p-value is regarded as statistically significant if its p-value is not greater than 0.025.

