# 2.8 Randomization of Trial Participants

Once the baseline evaluation is completed and eligibility is verified, consenting subjects will be randomly allocated in a 1:1 allocation to conventional or daily HD. The randomization schedules will be prepared by the Data Coordinating Center (DCC) prior to the start of recruitment.

Randomization will be stratified by Clinical Center and by diabetes status. Randomly permuted blocks of random sizes will be used to help balance numbers of participants assigned to both treatment regimens. This method guarantees that at no time during randomization will the participants in the individual groups be grossly unequal.

The randomization process will be centrally administered. All randomization schedules will remain confidential and known only by members of the Data Coordinating Center staff.

Once all baseline period studies have been completed, the forms corresponding to these studies have been received by the Data Coordinating Center, and the forms have been checked to be sure the patient meets eligibility requirements, the Principal Investigator or the study coordinator shall access the interactive randomization program. The program will verify through a defined set of questions that the participant is eligible and ready to be randomized and provide a randomized treatment assignment for that participant based upon his or her stratum. The randomization assignment will be displayed on the screen and emailed to the Clinical Center.

Randomization marks the participant's official and irrevocable entry into the Follow-up Period. Once a participant has been randomized, efforts will be made to conduct all evaluations irrespective of whether the subject starts the study treatment regimen or not, how long the patient continues on the

study treatment regimen, and how well the patient adheres to the study treatment regimen (see Section 7). These efforts should continue until termination of the Follow-up Period.

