#### 9.4 Main Secondary Outcomes

As described in Section 9.3, the PHC/Mortality and LV mass/Mortality composites are the coprimary endpoints for evaluation of patient benefit in the trial. In addition, as described in Section 5.1.2, main secondary outcomes have also been designated for each of seven specific and conceptually distinct physiological or quality of life-related outcome domains. These include: i) change over 12 months in the PHC; and, ii) change over 12 months in LV mass (without the mortality components), which represent the main secondary outcomes for evaluation of the physical function and cardiac structure and function domains, respectively. The remaining outcome domains and associated main secondary outcomes are iii) depression/disease burden (change over 12 months in Beck Depression Inventory), iv) nutrition (change over 12 months in serum albumin), v) cognitive function (change over 12 months in the Trail Making Test B), vi) mineral metabolism (change over 12 months in average pre-dialysis phosphorus), and vii) clinical events (rate of nonaccess hospitalizations or death). The primary evaluation of the effects of the treatment interventions on each of these seven outcome domains will be based on the designated main secondary endpoints. Analyses of other outcomes within each domain will be regarded as exploratory. Hypertension and anemia are also stipulated as main outcome domains, but are not conducive to the designation of a single main endpoint.

Two-sided tests will be used when testing the effects of the interventions on both the primary and secondary endpoints. The primary and main secondary analyses will be conducted by intention-to-treat in the sense that all patients analyzed according to their randomized assignment, irrespective of whether they adhered to the interventions. As noted above, however, follow-up will be censored at the time of renal transplantation. The analyses of the main secondary endpoints will be tested at the 0.05 level, without formal adjustment for multiple comparisons. However, nominally significant

effects on individual secondary outcomes will be interpreted as consistent with Type I errors unless accompanied by significant effects of the interventions on the primary outcomes and a consistent pattern of treatment effects across multiple secondary outcomes.

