### 9.9 Missing Data

In spite of the relatively short follow-up of 12 months, a nontrivial loss-to-follow-up is inevitable in a study of HD due to high rates of death, transplant, and patient transfer to non-participating facilities. In the HEMO Study the combined loss-to-follow-up from death, transplant, and transfer was approximately 18% at 1 year.

Because all methods for accounting for missing data depend on untestable assumptions [Verbeke, 2000], efforts will be made to minimize missing data in the study design and conduct of the trials [Allison, 2001]. These include: 1) continuing data collection after safety stop-points or patient-termination of the treatment regimens, 2) provisions to obtain the key outcome results at a later time point should the patient be hospitalized at the target time for the visits, 3) monitoring and feedback regarding missing data throughout the trial, and 4) oral administration of questionnaires.

Analytically, including prognostic baseline covariates and the early 4-month follow-up assessment should also reduce the chance of significant bias from missing data under the restricted maximum likelihood approach we propose. [2014 FHN Archive Note: FHN Executive Committee dropped prognostic covariates from the analyses.] In this approach, bias from missing data at the 12-month assessment is reduced to the extent that relationships between the unobserved values of missing responses and the probability of missingness can be accounted for by either the baseline factors or the observed 4-month responses. Nonetheless, some bias due to informative censoring [Little, 1995] is probably inevitable. Therefore, we plan to use a pattern mixture approach [Little, 1995] to perform sensitivity analyses of the estimated treatment effects under a range of assumptions regarding the association of the censoring times with the values of the missing responses [Daniels, 2000].

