# 9.11 Statistical Power

Estimates of parameters for determination of study power were obtained primarily from the HEMO Study database. During the first year of follow-up in the HEMO Study, the mortality rate was 12%/year, the transplant rate was 4%/year, the rate of all non-access hospitalizations was 1.19 per year, and approximately 80% of patients remained in active follow-up at the 1 year assessment. Data from the HEMO Study was also used to estimate the standard deviation of the change in the PHC, average serum albumin, and average serum phosphorus after controlling for the baseline value of outcome and pre-specified covariates. The standard deviation estimate of 24 g for the change in LV mass was estimated from the standard deviation of the change in LV mass by MRI obtained in 153 patients over 9 months by Pitt et al [Pitt, 2003].

The minimum detectable effect sizes for the co-primary PHC/Mortality and LV mass/Mortality composite endpoints were estimated under the following assumptions: a) the target sample size of 250 randomized patients is achieved, b) exponentially distributed survival, with a 12%/yr mortality rate in the control group, c) exponentially distributed transplantation, with a 4%/yr transplantation rate in both treatment groups, d) measurements at 12 months of the PHC and LV mass outcomes will be obtained in 80% of randomized patients, e) normally distributed changes in the PHC and LV mass

in those patients with 12-month measurements, with standard deviations (without covariate adjustment) indicated in Table 15a, f) utilization of the log rank test as described in Section 9.3, without covariate adjustment, and g) use of Hochberg's procedure to maintain an overall Type I error rate of  $\leq 5\%$ .

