**Estimated Detectable Effect Sizes for the Primary Outcomes (N = 250)** 

 As described in the text, under the Hochberg procedure the statistical power for each of the two primary outcomes depends in part on the effect size for the other outcome. Thus, the minimum detectable effect on the LVmass-Mortality composite is evaluated assuming treatment effects on the change in the PHC of either 0, 2.28 (corresponding to 25% of the estimated standard deviation of the change in the PHC score after covariate adjustment), or 4.56 units (corresponding to 50% of one standard deviation). Similarly, the treatment effects on the PHC-Mortality composite are evaluated assuming effects of either 0, 6 (25% of 1 SD) or 12 g on the change in LVmass. The simulation results indicate the above calculations are accurate if the correlation between the change in LVmass and the change in the PHC score is between 0 and +0.5.

Assumed SD of 1 Yr **Outcome Variable** 80% power 90% power Change PHC (points) 8.310 3.31 3.83 LV mass (g) 24.009.6 11.1 Average Albumin (g/dL) 0.296 0.12 0.14 Average serum phosphorus (mg/dL) 1.636 0.66 0.77 Beck Depression Inventory  $(1 \text{ SD})^2$ 0.40 0.46 Trail Making Test B  $(1 \text{ SD})^2$ 0.40 0.46

Table 15bEstimated Detectable Effect Sizes for the Main Secondary Outcomes  $(N = 250)^1$ 

 Treatment effect tested at alpha = 0.05 using a 2-sided test. The estimated minimum detectable reduction in rate of non-access hospitalization or death is 39% and 45% at 80% and 90% power, respectively.

 Detectable treatment effects expressed per 1 standard deviation of the changes in the Beck Depression Inventory and Trail Making Test B because pilot data on 1-year changes in these outcomes in dialysis patients is not available.

account information provided by the 4 month measurements for patients with missing data at 12 months, and in this respect are slightly conservative.

Assuming event rates in the control group of this trial are similar to those observed in the HEMO Study, that the relationship between non-access hospitalizations and death events are similar between the two trials, and that the loss-to-follow-up rates are also similar, the estimated minimum detectable reduction in rate of non-access hospitalization or death is 39% and 45% at 80% and 90% power, respectively.

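### The co-primary log-rank test ranks raw 12-month change without using the baseline value, forgoing up to about 7 points of power for the PHC composite; no gain can be derived for LV mass

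*Protocol*

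**What the plan says.** Section 9.3 builds each co-primary composite as one ranking. Deaths take the lowest places in order of survival time, and survivors follow in order of their change from baseline to 12 months. The arms are then compared: "The ranks will be compared between treatment groups using the log-rank test which allows the integration of both survival time and a quantitative measure". Neither the baseline value nor any other covariate is named. The power assumptions in 9.11, item (f), describe the same test: "utilization of the log rank test as described in Section 9.3, without covariate adjustment".

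Elsewhere the protocol uses baseline information:

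- Section 2.8: "Randomization will be stratified by Clinical Center and by diabetes status".
- Section 2.7 requires valid baseline results for every primary and main secondary endpoint before a patient can be randomized.
- Section 9.5 analyzes the changes in PHC and LV mass, as main secondary outcomes, with a model containing baseline value, Clinical Center, age and diabetic status.
- Table 15b gives the SD of change under that adjusted analysis and the effects detectable at 80% and 90% power. For PHC it reads "PHC (points) 8.310 3.31 3.83"; for LV mass the SD is 24.00 g.
- An archive note in 9.9, repeated in 2.7, reports: "FHN Executive Committee dropped prognostic covariates from the analyses". It does not say whether the baseline value of the outcome counts as one of these.

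**The concern.** Change from baseline is usually correlated with the baseline value through regression to the mean. A ranking of raw changes carries that avoidable variation, and chance baseline differences between arms feed into the result. Section 9.5 includes the baseline value and other covariates partly to reduce residual variability, yet the two outcomes that decide the trial do without them.

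The adjusted secondary analyses cannot make up for a missed primary. Under 9.4, an isolated nominally significant secondary result is read as compatible with a Type I error unless the primary outcomes are also significant. The power at stake is therefore in the primary tests themselves, and the data needed to recover it are already collected.

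**Working it through.** **Inputs from the protocol.** 250 patients, 1:1 ("the target sample size of 250 randomized patients is achieved"). Control mortality 12%/yr, reduced by 20% on daily HD. Transplantation 4%/yr in both arms. 12-month measurement in 80% of patients. Two-sided tests. Hochberg rule, so 0.025 applies to one composite when the other shows no effect.

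**SDs.**
- PHC behind Table 15a: the footnote equates 2.28 with 25% of one SD, so SD = 2.28/0.25 = 9.12.
- PHC in Table 15b: 8.310, described in 9.11 as controlling for baseline value and pre-specified covariates.
- LV mass behind Table 15a: 6/0.25 = 24 g. Table 15b also has 24.00 g.

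**Which PHC SD is unadjusted?** The Table 15a footnote labels the SD behind 2.28 as covariate-adjusted. Assumption (e) in 9.11 says the Table 15a SDs are unadjusted, and Table 15b gives 8.310 as the adjusted value. Simulating the unadjusted log-rank test at a 4.28-point effect gives power of 0.78–0.79 with SD 9.12 and 0.85 with SD 8.31. The table states 80%, so 9.12 is the SD that was used, and it is best read as unadjusted.

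**Reproducing the plan.** Simulation of the 9.3 test under the Hochberg rule used 4,000 trials per setting, an assumed correlation of 0.25 between the two changes, and no effect on the other outcome:

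| Composite | Effect | Stated power | Simulated |
|---|---|---|---|
| PHC | 4.28 | 80% | 79.3% |
| PHC | 4.96 | 90% | 89.3% |
| LV mass | 11.3 g | 80% | 80.6% |
| LV mass | 13.0 g | 90% | 89.7% |

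Table 15b also reproduces. With 100 measured per arm, PHC 3.31 gives 80.4% and LV mass 9.6 g gives 80.7%.

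**Adjusted PHC composite.** The variance ratio is (9.12/8.31)² = 1.20, so adjustment explains 1 − (8.31/9.12)² = 0.17 of the variance of change. As a shortcut, power ≈ Φ[(z_α + z_β) × 9.12/8.31 − z_α], with z_α = 2.241 for two-sided 0.025:
- From 80%: (2.241 + 0.842) × 1.0975 − 2.241 = 1.142, power 0.873.
- From 90%: (2.241 + 1.282) × 1.0975 − 2.241 = 1.625, power 0.948.

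Full simulation with the adjusted ranking gives 0.793 → 0.861 at 4.28 points and 0.893 → 0.941 at 4.96. A separate run with residual ranks, at a fixed 0.025, gives 0.778 → 0.847 and 0.884 → 0.933. The effect detectable with 80% power falls from about 4.3 to about 4.0 points. Simulated Type I error was 0.024–0.026 with and without adjustment.

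**Adjusted LV mass composite.** With 24 g both before and after adjustment, power at 11.3 g is 80.6% → 79.8%, which is no gain. If baseline is assumed to explain some variance, residual ranks at a fixed 0.025 give:

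| Assumed share explained | Unadjusted | Adjusted |
|---|---|---|
| 0 | 0.768 | 0.767 |
| 0.05 | 0.780 | 0.801 |
| 0.10 | 0.785 | 0.821 |
| 0.17 | 0.792 | 0.858 |
| 0.30 | 0.796 | 0.910 |

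**Stratifying the log-rank test.** With about 10 centers and two diabetes strata (20 cells), PHC power at 4.28 points falls from 0.778 to 0.739 if the cells are not prognostic, and from 0.790 to 0.768 if they explain 5% of the variance.

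**The case against.** The strongest reply is that nothing here is wrong. The unadjusted test is disclosed, the sample size was computed for it, and it delivers the power claimed. Chance baseline imbalance is already covered by the Type I error, and baseline-adjusted analyses of both changes are pre-specified as main secondary outcomes. All of this stands, and it makes the point one of efficiency. It does not remove the point, because 9.3 and 9.11(f) together fix the less efficient choice.

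A reader might compare the PHC effects detectable at 80% power, 4.28 in Table 15a and 3.31 in Table 15b, and put the whole gap down to missing adjustment. The figures do not support that. Adjustment recovers about 0.3 of the 0.97 points; most of the rest reflects the 0.025 threshold and the rank composite with deaths.

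A reader might also infer that leaving out the stratification factors costs power. It was not shown to. Stratifying on all cells costs about 2 to 4 points, and stratifying by diabetes alone added nothing where diabetes was assumed not prognostic.

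Two further objections stand as limits. The 17% reduction in PHC variance reflects baseline value plus covariates, and the protocol does not give the share due to baseline alone. If the archive note removes some covariates, part of the gain may go with them. Residual ranking also relies on a regression fitted only to measured survivors and leaves deaths unadjusted.

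**Conclusion.** The point holds as forgone efficiency in a valid, adequately powered test. For the PHC composite, adjustment is worth up to about 7 percentage points at the 80% design point and about 5 at the 90% point. This rests on 9.12 being the unadjusted SD, which the reproduced power supports against the footnote's label, and on the full reduction to 8.310 being available.

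It is tempting to give the same figure for both composites, but the documents do not support that. The LV mass SD is 24 g in both tables. Nor does that equality prove that there is no gain, because 9.11 takes the 24 g from the SD of change in an external 9-month study. The gain for LV mass is unknown: about 0 if baseline explains nothing, and about 4 to 8 points if it explains 10–20% of the variance.

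**What to change.** In 9.3, keep deaths ranked below survivors. Rank survivors on the residual from one pooled regression of 12-month change on baseline value, fitted without the treatment term, with diabetes and Clinical Center as further regression terms. Then apply the log-rank test as now. Do not stratify the test on all center-by-diabetes cells. Stratifying by diabetes alone is optional, and no power gain is claimed for it.

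Rerun Table 15a for this test, correct the footnote's description of the 9.12 SD, and state that the archive note leaves the baseline value of the outcome in place.

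The cost is one revised paragraph, a rerun of the power simulation and two clarifications. No new data are needed. The downsides are a slightly less transparent rank scale and that deaths remain unadjusted.
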